3.2 STUDY TREATMENT

The patients will be assigned to one of two treatment group in 1:1 ratio:

- Group 1. OKITASK® 40 mg – 35 patients
- Group 2. Placebo – 35 patients

The patient will assess pain by VAS at 0' – immediately before study drug dosing.

Upon study drug administration the patients will immediately start two stopwatches. One of them will be stopped once the patient feels first perceptible pain relief; the second one will be stopped once the patient feels the meaningful pain relief.

The patient will stay at the site for 6 hours post-dose for pain and AE assessment. Pain intensity will be assessed by VAS at 5', 10', 15', 30', 45', 60' (1 hour), 90' (1.5 hours), 120' (2 hours), 180' (3 hours), 240' (4 hours), 300' (5 hours), and 360' (6 hours) post-dose.

Pain relief will be assessed by VAS at 5', 10', 15', 30', 45', 60' (1 hour), 90' (1.5 hours), 120' (2 hours), 180' (3 hours), 240' (4 hours), 300' (5 hours), and 360' (6 hours) post-dose.

Patients should mark actual time points of VAS measurement. Deviations from planned time points will not be considered as protocol deviations. Only omitted values will be considered as protocol deviations.

Patients' overall assessment will be performed right before the discharge from the site.

Follow-up phone call to the patient to assess AEs will be performed on Day 3 (48 hours

after the study drug dosing). Any SAE spontaneously reported by the patient within 30 days of dosing will be collected.

Should the patient require rescue medication at any time during 6 hours post-dose, the last VAS measurement and patient's overall assessment will be performed before the rescue medication dosing.

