7. REPLACEMENT OF THE MISSING DATA

7.1 PRIMARY EFFICACY

Considering that the primary variable AUC_{0-6h} is derived from pain intensity VAS measurements, analyses on primary and secondary variables without or with substitution of missing data, using the last observation carry forward (LOCF) methodology, has been considered in order to avoid bias in the inferential testing of treatment effect.

For LOCF analysis substitution of missing data will be applied only on all patients that have at least one VAS value post-baseline (patient compliant with ITT population definition). Missing post-baseline pain score will be replaced with previous one. **Baseline data (pre-dose) could be carried forward also.** Possibility to use baseline data comes from the data nature, which seems to be linearly decreasing over time. This will allow to calculate AUC in case of missing first post-baseline value (5 minutes).

If data be missing more than one time point after baseline, the data will be qualified as invalid. Consecutive missing values will be replaced with the last non-missing (observed) value. If more than two time points data are missing and after missing data some points have values (non-missing), then all missing sequence will be replaced with last non-missing value. In case of absence non-missing values after two missings, no replacement will be done and data will be find invalid for analysis. Possible cases are presented in table below:

¹ Cite from the Study Protocol

² SAS 9.2 <http://support.sas.com/documentation/92/>

Table 7.1 LOCF missing data replacement cases

Time points	Scale	Scale LOCF	AUC
0 (baseline)	A	A	Valid
1	B	B	
2	.	B	
3	.	B	
4	C	C	
5	D	D	
0 (baseline)	A	A	Valid
1	.	A	
2	B	B	
3	C	C	
4	D	D	
5	E	E	
0 (baseline)	A	A	Invalid
1	.	.	
2	.	.	
3	B	B	
4	C	C	
5	D	D	
0 (baseline)	A	A	Valid
1	B	B	
2	.	B	
3	.	B	
4	.	B	
5	C	C	
0 (baseline)	A	A	Invalid
1	B	B	
2	C	C	
3	.	.	
4	.	.	
5	.	.	

For the sensitivity analysis the fully conditional specification (FCS) regression method¹ will be used for replacing missing data.

SAS code example:

```
proc mi data=pain round=1. seed=139592 out=pain_imp;
  class trt;
```

¹ Van Buuren 2007; Brand 1999; Rubin 1987

http://documentation.sas.com/?docsetId=statug&docsetTarget=statug_mi_details07.htm&docsetVersion=14.3&locale=en

² Could be any other

```

fcs nbiter=20 reg (pain=time trt time*trt/details);
var pain time trt;
run;

```

Pain dataset description:

Alphabetic List of Variables and Attributes						

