9.2 DEMOGRAPHICS AND BASELINE CHARACTERISTICS

Demographic data and baseline characteristics will be presented using descriptive statistic for the ITT analysis populations.

Following parameters will be presented at screening:

- Age
- Gender
- Height
- Weight
- BMI
- Race
- Medical history
- Concomitant diseases
- Previous therapy
- Pregnancy test (for females)
- Oral cavity examination (only abnormal parameters)
- Vital signs (only abnormal parameters)

Between groups comparisons will be performed for:

- Age (ANOVA from LME model)
- Gender

¹ Baseline is Day 1 time 0 minutes

Number and percent of patients with previous medications will be presented as a frequency arrays by ATC (3 and 5 levels) and treatment groups.

Current and history diagnoses will be coded by MEDDRA dictionary. Data will be presented by SOC (System Organ Class) and PT (Preferred Term).

Frequencies of CS¹ oral cavity examination abnormalities at Day 1 will be summarized with descriptive statistics (absolute and relative frequencies). Table will show only CS abnormalities. No between group tests are planned.

Frequencies of CS vital signs abnormalities at Day 1 will be summarized with descriptive statistics (absolute and relative frequencies). Table will show only CS abnormalities. No between group tests are planned.

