10.1 PRIMARY EFFICACY VARIABLE

Primary variable will be the AUC_{0-6h} without or with LOCF of pain intensity profile between time 0 (baseline value of VAS) and 6 hours post-treatment. AUC_{0-6h} analysis will be based on **actual rather than scheduled timings** and will be calculated using the trapezoidal rule:

$$\sum \frac{P_n + P_{n-1}}{2} (t_n - t_{n-1})$$

where, P_n – pain intensity at point n, t_n – time point n.

Treatment AUCs will be compared using ANOVA methodology (simple GLM model). In case of significant covariates discovered during baseline data analysis, such covariates could be added to the ANOVA model (level to stay 0.15). F-test for type III treatment effect will be used for testing the Null hypothesis.

Null hypothesis (H_0) that OKITASK® is no different from Placebo will be rejected and alternative hypothesis (H_1) that OKITASK® is superior to Placebo will be accepted if mean AUC_{0-6h} (OKITASK®) is less than mean AUC_{0-6h} (Placebo) and $p < 0.05$.

$$H_0: \mu_T = \mu_R$$

$$H_1: \mu_T \neq \mu_R$$

where μ_T – OKITASK® (**Test**) mean AUC_{0-6h} ; μ_R – Placebo (**Reference**) mean AUC_{0-6h} .

If the actual time is not recorded, the scheduled time will be used instead. LOCF approach will be applied as described in Section 7.

Additional test on FCS replaced data will be performed to confirm analysis of the LOCF data (sensitivity).

For the PP population data could not be missing. There were no LOCF or other methods applied.

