10.2 SECONDARY EFFICACY

Secondary efficacy variables will be analyzed only for ITT population.

¹ Clinically significant

AUC_{0-6h} without or with LOCF of pain relief profile between time 0 (baseline value of VAS) and 6 hours post-treatment. AUC_{0-6h} analysis will be based on **actual rather than scheduled timings** and will be calculated using the trapezoidal rule (see as per primary variable).

Pain profile – Pain intensity profile will be analyzed using Analysis of Variance (ANOVA) for repeated measurements. The model will include fixed effect terms for clinical site, time point and treatment. Time point will be specified as a repeated measurement. In order to select an appropriate matrix for the observations within each subject, 3 models will be fitted using the compound symmetry, Huynh-Feldt and unstructured structures. The matrix for the final model will be selected using Akaike's Information Criterion where the lowest value indicates the best fit. The importance of the treatment-by-site interaction will be investigated but if the term is not significant at the 10% level, it will be excluded from the final model. The adjusted least squares mean will be estimated for each combination of time point and treatment. The estimated treatment difference between OKITASK® and placebo at each time point will be presented together with the corresponding 95% confidence interval. Pain profile will be analyzed based on **scheduled rather than actual timings**.

SAS code example:

```
proc mixed data=locf method=REML order=internal1;
  class patid site trt time;
  model pain = trt time trt*time
    site trt*site/ intercept ddfm=satterth;
  repeated time/ type=CS2 subject=patid(trt);
  lsmeans trt*time/ diff=all cl;
run;
```

Pain relief – Pain relief will be analyzed in the same way.

LOCF replaced data of pain intensity and pain relief will be presented graphically by treatments and time points.

Time to first perceptible relief (TFPR)³ – Kaplan-Meier curve and Log rank test will be used to describe and test treatment profile differences. In table it will be presented with median, 95% CI and p-value from Log rank test.

Time to meaningful pain relief (TMPR)⁴ – Kaplan-Meier curve and Log rank test will be used to describe and test treatment profile differences. In table it will be presented with median, 95% CI and p-value from Log rank test.

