12.2.2 Secondary efficacy

Table 12.13 secondary efficacy. Visual Analogue Scale. Pain Intensity Assessment with LOCF. ITT population. N = XX

Parameter Treatment	Result				
	N	Mean (SD)	Median	Min	Max
Visual Analogue Scale. Pain Intensity. AUC_{0-6h}. LOCF					
OKITASK [®]	XX	XX.X (XX.X)	XX.X	XX.X	XX.X
PLACEBO	XX	XX.X (XX.X)	XX.X	XX.X	XX.X
p-value ANOVA = 0.***					
Visual Analogue Scale. Pain Intensity. AUC_{0-6h}. Multiple Imputation					
OKITASK [®]	XX	XX.X (XX.X)	XX.X	XX.X	XX.X
PLACEBO	XX	XX.X (XX.X)	XX.X	XX.X	XX.X
p-value ANOVA = 0.***					

Table 12.14 secondary efficacy. Visual Analogue Scale. Pain Intensity Assessment with LOCF. ITT population. N = XX

Parameter Treatment	Result				
	N	Mean (SD)	Median	Min	Max
Visual Analogue Scale. Pain Intensity. AUC_{0-6h}. LOCF					
OKITASK [®]	XX	XX.X (XX.X)	XX.X	XX.X	XX.X
PLACEBO	XX	XX.X (XX.X)	XX.X	XX.X	XX.X
p-value ANOVA = 0.***					
Visual Analogue Scale. Pain Intensity. AUC_{0-6h}. Multiple Imputation					
OKITASK [®]	XX	XX.X (XX.X)	XX.X	XX.X	XX.X
PLACEBO	XX	XX.X (XX.X)	XX.X	XX.X	XX.X
p-value ANOVA = 0.***					

Table 12.15 Secondary efficacy. Visual Analogue Scale. Pain Intensity profile. ITT population. N = XX

Parameter Treatment	Day 1 time	Results				
		N	Mean (SD)	Median	Min	Max

Parameter Treatment	Day 1 time	Results				
		N	Mean (SD)	Median	Min	Max
Visual Analog Scale. Pain intensity						
OKITASK®	0 min. Baseline	xx	xx.x (xx.x)	xx.x	xx.x	xx.x
PLACEBO	0 min. Baseline	xx	xx.x (xx.x)	xx.x	xx.x	xx.x
$\mu_T - \mu_R$ 95% CI			xx.x [xx.x; xx.x]			
OKITASK®	5 minutes	xx	xx.x (xx.x)	xx.x	xx.x	xx.x
PLACEBO	5 minutes	xx	xx.x (xx.x)	xx.x	xx.x	xx.x
$\mu_T - \mu_R$ 95% CI			xx.x [xx.x; xx.x]			
...						
OKITASK®	6 hours	xx	xx.x (xx.x)	xx.x	xx.x	xx.x
PLACEBO	6 hours	xx	xx.x (xx.x)	xx.x	xx.x	xx.x
$\mu_T - \mu_R$ 95% CI			xx.x [xx.x; xx.x]			

Figure 12.1 Secondary efficacy. Visual Analogue Scale. Pain Intensity profile. ITT population. N = XX

[figure not shown]

Figure 12.2 Secondary efficacy. Visual Analogue Scale. Difference in Pain Intensity means with 95% CI. ITT population. N = XX

[figure not shown]

Table 12.16 Secondary efficacy. Visual Analogue Scale. Pain Relief profile. ITT population. N = XX

Parameter	Treatment	Day 1 time	Results				
			N	Mean (SD)	Median	Min	Max
Visual Analog Scale. Pain relief							
OKITASK [®]	0 min. Baseline	xx	xx.x (xx.x)	xx.x	xx.x	xx.x	xx.x
PLACEBO	0 min. Baseline	xx	xx.x (xx.x)	xx.x	xx.x	xx.x	xx.x
$\mu_T - \mu_R$	95% CI		xx.x [xx.x; xx.x]				

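### The pain-intensity profile model makes no use of the pre-dose VAS, so its post-dose differences carry part of any chance pre-dose imbalance and lose precision

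*SAP*

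**What the plan says.** In words, section 10.2 specifies: "The model will include fixed effect terms for clinical site, time point and treatment". The example code beneath it begins "model pain = trt time trt*time" and adds site and treatment by site. It is fitted to the LOCF data with time as the repeated factor, and least squares mean differences are taken from treatment by time. On what is reported, the section says: "The estimated treatment difference between OKITASK® and placebo at each time point will be presented together with the corresponding 95% confidence interval". Neither the text nor the code contains pre-dose pain as a covariate, and the response is the pain score itself rather than a change.

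A footnote to the ITT definition in section 8.1 (printed on the page with section 9.2) fixes the reference point: "Baseline is Day 1 time 0 minutes". Section 3.2 places that reading "immediately before study drug dosing".

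The shell of Table 12.15 (section 12.2.2) opens with a row labelled "0 min. Baseline" for each arm, followed by a treatment difference with a 95% CI, and then the 5-minute rows in the same form.

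The SAP's only covariate provision is in section 10.1. It is conditional, has a level to stay of 0.15, and is written for the AUC ANOVA. Section 9.2 limits between-group baseline comparisons to age and gender. Section 7.1 adds, on missing readings: "Baseline data (pre-dose) could be carried forward also".

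**The concern.** Treatment cannot have affected a reading taken before dosing, so any difference between the arms at time 0 is chance. A model with a free treatment-by-time term and no baseline information cannot use that fact. Each post-dose difference is then in essence the site-adjusted difference in raw arm means, including whatever imbalance was there before dosing.

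The pain profile over time is a stated secondary objective (section 5.2). Pre-dose and post-dose readings should be most alike at 5, 10 and 15 minutes, so the carried share and the lost precision should be largest there. Where a missing 5-minute reading is filled with the pre-dose value, that patient's time-0 score passes into the first post-dose point in full.

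**Working it through.** **The plan's own figure.** The SAP states no precision or sample size for the profile model. Its only sample-size figure is for the primary AUC (section 6: difference 90, SD 121, two-sided alpha 0.05, power 80%). n per arm = 2 × (1.96 + 0.84)² × 121² / 90² = 28.4, rounded up to 29, or 58 in total, as stated. Allowing for 15% drop-out, 58 / 0.85 = 68.2, so 69 against the stated 70. The 35 per arm used below is the planned enrolment.

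**Assumed inputs.** The SAP gives no SD for a single VAS reading and no correlation between readings. I take SD 10, 15 or 20 mm and rho 0.5, 0.7 or 0.9. Entry requires a VAS of about 30 mm or more on a 100 mm scale (sections 3.1 and 3.4). An even spread over 30 to 100 would have SD 70/√12 = 20 mm, so these SDs are not extreme.

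**Step 1: size of the chance pre-dose difference.** SE = SD × √(2/35).

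| Assumed SD (mm) | SE (mm) | 95% range (mm) |
|---|---|---|
| 10 | 2.4 | ±4.7 |
| 15 | 3.6 | ±7.0 |
| 20 | 4.8 | ±9.4 |

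**Step 2: share carried forward, and what adjustment gains.** With complete data and a full treatment-by-time term, the estimated difference at time t is the difference in arm means at t. Given a pre-dose difference D0, its expectation is the true effect plus rho × (SD at t / SD at 0) × D0. With equal SDs the share is rho. This holds whether or not time 0 is a level of the response. Baseline adjustment removes the share and multiplies the SE by √(1 − rho²). The last column takes SD 15 mm at every time; the planned 95% half-width is then 1.96 × 3.59 = 7.0 mm.

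| Assumed rho | Share carried | SE multiplier after adjustment | Adjusted half-width (mm) |
|---|---|---|---|
| 0.5 | 0.5 | 0.87 | 6.1 |
| 0.7 | 0.7 | 0.71 | 5.0 |
| 0.9 | 0.9 | 0.44 | 3.1 |

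**Step 3: simulation check.** 4000 simulated trials, 35 per arm, SD 20 mm, no treatment effect, no site term.

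- Compound symmetry, rho 0.7: carried share about 0.70 at the times checked (5, 10, 15 and 360 minutes). The SE is about 4.8 mm as planned and 3.5 mm adjusted.
- Correlation falling with time (about 0.94 at 5 minutes): carried share 0.93, 0.92 and 0.90 at 5, 10 and 15 minutes, and 0.35 at 6 hours. The SE falls from 4.8 to 1.7 mm at 5 minutes, but only from 4.8 to 4.5 mm at 6 hours.
- With adjustment the carried share was about 0 in every case.

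**Step 4: what this means for one trial.** Under no treatment effect, if the chance pre-dose difference happens to be 2 SE, the unadjusted later interval excludes zero with probability about 13%, 22% or 36% at rho 0.5, 0.7 or 0.9. If it happens to be 1 SE, the figures are about 4.8%, 3.9% and 0.8%. Over all possible imbalances they average to the nominal 5%.

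**The case against.** Several objections are sound and limit the point.

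- **The planned analysis is valid.** Randomisation makes the unadjusted differences unbiased on average, and their intervals keep nominal coverage. A reader might infer from the carried imbalance that the intervals are wrong; they are not. What remains is bias conditional on the imbalance that occurs, and lost precision.
- **Time 0 as a response level is not stated outright.** Section 10.2 does not list the time levels, and its code is an example. The evidence is the shell of Table 12.15. Table 12.16 prints the same 0-minute row for pain relief, which section 3.2 schedules only from 5 minutes, and a footnote to section 12 allows the final tables to differ. The shell suggests that time 0 is a response level but does not prove it. A further inference, that the pre-dose reading distorts the 10% treatment-by-site test, depends on the same reading and has not been quantified.
- **Onset has its own endpoints.** It is tempting to say that evidence of onset is compromised. Time to first perceptible relief and time to meaningful relief are timed by stopwatch and analysed by Kaplan-Meier and log-rank, outside this model. The SAP attaches no test or decision rule to the 5, 10 or 15 minute differences.
- **Near-complete carry-over needs rho near 0.9.** That is plausible for readings minutes apart but undocumented, and the entry threshold may lower both the baseline SD and the correlation.
- **The imbalance would be visible** if the Table 12.15 shell is followed. That helps a reader notice it, but neither corrects the later estimates nor narrows their intervals.

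None of this answers the core point. The model ignores a pre-dose measurement that the trial collects, and the later differences carry the imbalance on either reading of the shell.

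**Conclusion.** The point holds as a modest one about a secondary analysis. The profile model discards pre-dose VAS, so each post-dose difference carries about rho of any chance pre-dose difference, and its SE is larger than it need be by a factor of 1/√(1 − rho²). Over assumed rho of 0.5 to 0.9, adjustment would cut the SE by 13% to 56%, with the most gain expected early and little by 6 hours if the correlation fades. These sizes rest on assumed SDs and correlations, equal SDs over time and essentially complete data. The result is not that the planned intervals are invalid, or that the trial's onset evidence fails. The primary AUC test is a separate model and is not affected.

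**What to change.** Choose one of the following for the pain-intensity profile in section 10.2, and state the time levels of the response explicitly:

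1. Model only the 12 post-dose readings, with time-0 VAS and time-0 VAS by time as covariates.
2. Keep time 0 in the response, but constrain the two arm means to be equal there. The adjustment then depends on the covariance structure selected: compound symmetry would impose one correlation at every time, so option 1 is the simpler choice.

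In Table 12.15, show time 0 descriptively by arm, without a model-based difference and CI. Any imbalance stays visible.

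The cost is a small change to the model code, one changed row of the shell and no new data. Option 1 adds up to 12 slopes, which is not nothing with about 70 patients and an unstructured matrix among the candidates (12 × 13 / 2 = 78 parameters for 12 readings), but is modest against the gain.

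### The only code for the pain-profile mixed model runs on LOCF-filled data, and no run on observed readings is specified; the effect is small and secondary, and the remedy is cheap.

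*SAP*

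**What the plan says.** Section 10.2 analyses the pain-intensity profile with a repeated-measures model: "Time point will be specified as a repeated measurement". Compound symmetry, Huynh-Feldt and unstructured covariances are compared by AIC, and scheduled times are used. The prose on the model names no input dataset. The code example does: "proc mixed data=locf method=REML". For the second profile the section adds: "Pain relief will be analyzed in the same way". The one prose mention of LOCF for the profiles concerns the figures: "LOCF replaced data of pain intensity and pain relief will be presented graphically by treatments and time points".

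Section 7.1 leaves the general position open, planning "analyses on primary and secondary variables without or with substitution of missing data". Its filling rule is "Missing post-baseline pain score will be replaced with previous one", and "Baseline data (pre-dose) could be carried forward also". The reason given for using baseline is: "Possibility to use baseline data comes from the data nature, which seems to be linearly decreasing over time". Table 7.1 sets the limits: interior gaps are filled whatever their length, a single missing first reading is filled from baseline, and a run of missing readings at the end is not filled.

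**The concern.** Section 7.1 motivates LOCF by the AUC, which needs a value at each point of the trapezoid. That reason does not carry over to a likelihood model with a within-patient covariance, which takes each patient's observed readings as they are and is valid under missing at random (MAR) without filling.

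When such a model is fed filled data, each copy has the weight of a measurement. If pain is falling, as section 7.1 expects, a carried value is too high, and more so in the arm that falls faster. While the arms are diverging, the difference at a time point is therefore pulled toward the smaller, earlier difference. The standard error also counts the copies as information, and they enter the AIC comparison of covariance structures. At stake are the time-point differences and 95% confidence intervals for two secondary profiles.

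**Working it through.** **What the plan fixes.** The SAP states no figure for this model. The code names the LOCF dataset, the prose names none, and section 7.1 allows both. Multiple imputation appears only for AUC results (section 10.1; Tables 12.9, 12.11, 12.13 and 12.14). So LOCF is the only input actually named for the profile model.

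**Which readings get filled (section 7.1, Table 7.1).**
- Interior gap followed by a later reading: filled, whatever its length (one case fills three points).
- Single missing 5-minute reading: filled from baseline.
- Two missing readings directly after baseline: not filled.
- Two or more missing readings at the end: not filled. By section 3.2 the last VAS is taken before rescue, so most post-rescue readings fall here.
- Single missing last reading: not shown in the table; the general rule would fill it.

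**Shift in the difference, by hand.** Inputs from section 6: AUC0-6h of 263 and 173 mm h, difference 90. Assumptions: a common baseline, linear decline, and a fraction f of post-dose readings missing at random, all filled.
- The difference grows as d(t) = s·t, with area s·6²/2 = 18s. Setting 18s = 90 gives s = 5 mm/h, so d(3 h) = 15.0 mm. The baseline value cancels.
- The expected difference after LOCF is L_k = (1 − f)·d_k + f·L_(k−1), with L_0 = 0, over 5, 10, 15, 30, 45, 60, 90, 120 and 180 minutes.
- For f = 0.10: L(1.5 h) = 7.24; L(2 h) = 0.9 × 10 + 0.1 × 7.24 = 9.72; L(3 h) = 0.9 × 15 + 0.1 × 9.72 = 14.47.

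| f | L at 3 h (mm) | Loss (mm) | Loss (%) |
|---|---|---|---|
| 0.03 | 14.85 | 0.15 | 1.0 |
| 0.05 | 14.74 | 0.26 | 1.7 |
| 0.10 | 14.47 | 0.53 | 3.5 |

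**Standard error.** If a patient's other readings said nothing about a missing one, 10% missing would make the filled-data SE too small by the factor √0.9 = 0.95, about 5%. Within-patient correlation makes the true gap smaller. If neighbouring readings explained 70% of the variance (an assumption), the observed-data SE would exceed the filled-data SE by √(1 + 0.111 × 0.3) = 1.016, about 1.6%.

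**Simulation check.** Assumptions: 35 per arm, 13 time points, unstructured covariance, SD 20 mm per reading, mean profiles with AUC 265 and 172, 150 runs per scenario. The methods were compared on the same simulated data.
- 5% intermittent gaps: 4.9% of post-dose readings are copies. The difference moves toward zero by 0.23 mm at 0.5 h (bias −0.32 to −0.09) and 0.24 mm at 1 h (−0.69 to −0.45).
- 15% gaps: 14.3% are copies. The shifts are 0.61 mm at 0.5 h and 0.74 mm at 1 h. The model SE at 6 h falls from 4.94 to 4.83, a ratio of 0.978, about 2%.
- 5% gaps plus rescue-driven stopping: the Table 7.1 rule moves the 6 h difference by 0.25 mm (bias −0.03 to −0.28), here away from zero. Filling every gap, which Table 7.1 does not do, would move it 2.30 mm away from zero (−0.03 to −2.33).

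The pull toward zero thus belongs to times when the arms are diverging. Late in the profile, or with carrying forward after rescue, the sign can reverse.

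**The case against.** The code is headed as an example, and section 7.1 permits analysis without substitution. Tables 12.15 and 12.16 are not titled as LOCF tables, whereas Tables 12.9, 12.11, 12.13 and 12.14 are. That stands in part: the SAP does not firmly prescribe LOCF for this model. But leaving the input open is itself a gap, and the only concrete instruction points to the filled data.

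The effect is also small: tenths of a millimetre on a 100 mm scale, against a simulated standard error near 5 mm. Patients stay on site for six hours and omitted readings count as deviations, so long interior gaps should be uncommon. This stands, and it limits the weight of the point. No size has been established for the influence on the AIC choice.

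Three stronger readings are tempting but not supported:
- A reader might infer that post-rescue readings are invented wholesale. Table 7.1 leaves two or more trailing missing points unfilled.
- A reader might infer that patients marked Invalid lose their observed readings. That label stands in the AUC column, and the filled-scale column keeps their observed values. The prose of section 7.1, which calls such data invalid for analysis, is ambiguous, so this is a matter to clarify rather than an established loss.
- A reader might take a 5% understatement of the standard error as the estimate. It is an upper bound at 10% missing that ignores within-patient correlation.

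**Conclusion.** The point holds as a modest improvement to a secondary analysis. The sole code for the profile model uses LOCF data, no observed-data run is specified, and the model does not need filling. The expected distortion is about 0.1-0.5 mm at 3 h for an assumed 3-10% of readings missing, and about 2% in the 6 h standard error for an assumed 15% of gaps. The missingness rates, the linear profiles and the SD per reading are assumptions; the SAP gives none of them except the planning AUCs and an expected, roughly linear fall in pain. It would be wrong to infer bias in the primary result from this: the primary test is the AUC ANOVA of section 10.1, which this model does not feed.

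**What to change.** In section 10.2, name the input of both profile models as all observed readings of all ITT patients at scheduled times, without filling, and change the dataset in the code to match. State that the AUC label Invalid in Table 7.1 does not remove a patient's observed readings from these models. Keep any LOCF run as a labelled supportive analysis. If the figures stay on LOCF data, their titles should say so; otherwise draw them from the observed-data model.

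The cost is one dataset name and a sentence or two. N will vary by time point, and Tables 12.15 and 12.16 already have an N column for this. The model relies on MAR, which should be stated. It does not by itself settle how readings after rescue are to be treated, so the SAP should say that separately.

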3. STUDY DESIGN

This is a multicenter, double-blind, randomized, parallel groups, placebo-controlled study to assess the efficacy and safety of OKITASK® 40 mg granules in patients with acute pain syndrome after removal of molar teeth. The study will be conducted at 3-6 Russian sites. A total expected number of enrolled subjects is 70 (35 per each group). Patients' enrollment to the sites is competitive.

The study will consist of three periods: screening, study treatment and follow-up.

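### If the unstructured covariance is selected and post-rescue readings stay blank, the Satterthwaite option leaves the 4–6 h confidence intervals of the pain and relief profiles somewhat too narrow

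*SAP*

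**What the plan says.** Section 10.2 (Pain profile) specifies a repeated-measures model in which "3 models will be fitted using the compound symmetry, Huynh-Feldt and unstructured structures", and the lowest AIC decides. The code example is PROC MIXED by REML on `data=locf`, with the options "site trt*site/ intercept ddfm=satterth". It prints `type=CS`, and a footnote allows HF or UN in its place. Treatment differences with 95% CIs are reported at every scheduled time, and pain relief is handled the same way.

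The readings come from section 3.2: one before dosing ("The patient will assess pain by VAS at 0") and twelve after it (starting "Pain intensity will be assessed by VAS at 5', 10', 15', 30', 45', 60' (1 hour", then on to 6 h). Table 12.15 shows baseline as a row of the profile, so there are 13 times. On sample size, section 3 says "A total expected number of enrolled subjects is 70 (35 per each group").

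Two passages decide what is missing late in the profile. Section 3.2 says that on rescue "the last VAS measurement and patient's overall assessment will be performed before the rescue medication dosing". Section 7.1 says of trailing gaps: "In case of absence non-missing values after two missings, no replacement will be done and data will be find invalid for analysis". The last case in Table 7.1 keeps the early values, leaves the trailing ones blank, and puts the invalid label in the AUC column.

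**The concern.** The Satterthwaite method changes the reference t distribution but not the SE, which is computed as if the fitted covariance matrix were the true one. With complete, nearly balanced data this costs almost nothing, because the estimated time-point differences hardly depend on the covariance. When late readings are missing, the model recovers the late means through the estimated correlation with earlier readings, and the uncertainty of that correlation is left out of the SE.

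Rescue produces this pattern: readings end at different times, probably more often on placebo. At stake are the intervals at 4–6 h, which a reader would use to judge how long the effect lasts. They are secondary, and no decision rule hangs on them.

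**Working it through.** **The plan's own figure.** The SAP gives no figure for the profile model, so I checked the sample size that feeds it (section 6: difference 90, SD 121, power 80%, α 0.05 taken as two-sided). n per arm = 2 × (1.960 + 0.842)² × 121² / 90² = 28.4, so 29 per arm and 58 in total. 29 / 0.85 = 34.1, so 35 per arm and 70 enrolled. Both agree with the SAP.

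**Covariance parameters at 13 times.** UN: 13 × 14 / 2 = 91. HF: 13 + 1 = 14. CS: 2. First-order ante-dependence, ANTE(1): 13 + 12 = 25.

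**Simulation 1.** 35 per arm, 4 sites (section 3: "The study will be conducted at 3-6 Russian sites"), UN by REML. Assumptions not in the SAP: VAS SD 15–26 mm, correlation falling with lag, rescue from 1 h driven by the last observed VAS, and post-rescue readings blank with earlier ones kept. KR is Kenward-Roger and Satt is Satterthwaite.

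| Rescued, placebo / active | KR SE ÷ Satt SE at 4 / 5 / 6 h | Satt coverage at 4 / 5 / 6 h | KR coverage at 6 h |
|---|---|---|---|
| none | 1.002 / 1.002 / 1.002 | 94.8 / 95.0 / 94.5% | 94.8% |
| 23% / 12% | 1.009 / 1.012 / 1.015 | 94.5 / 94.8 / 93.2% | 93.5% |
| 53% / 34% | 1.031 / 1.041 / 1.052 | 93.8 / 94.8 / 93.4% | 94.6% |
| 74% / 55% | 1.069 / 1.091 / 1.113 | 92.4 / 90.7 / 86.0% | 89.5% |

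Monte Carlo error is about 1 point, and up to 2 in the last row. That row uses converged fits only: 156 of 500 did not converge (in the simulation's algorithm, not SAS). In it the Satterthwaite SE at 6 h was 8.16 against an actual spread of 10.77 (8.16 / 10.77 = 0.76). The Kenward-Roger SE was 9.09 (9.09 / 10.77 = 0.84), so it closes only part of the gap.

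**Simulation 2.** Planning AUC means 263 and 173, AUC SD 120, correlation 0.30 + 0.65 × exp(−lag / 2.5 h). Coverage at 6 h, Satterthwaite then Kenward-Roger, by placebo / active rescue:
- 13% / 5%: 95.0% (Satterthwaite).
- 33% / 16%: 93.9%, 94.6%; SE 5% too small.
- 58% / 33%: 91.7%, 93.4%; SE 8.28 against 9.58, which is 14% too small.
- 77% / 51%: 84%, 90%.

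**Which structure AIC picks (simulation 1).** UN in 100 of 100 fits when correlation fell with lag, and in 0 of 149 under true compound symmetry.

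**Other readings of the data set (simulation 1, 53% / 34% rescued).** KR SE ÷ Satt SE at 4–6 h is 1.007–1.008 if rescued patients are excluded and 1.002 if all trailing gaps are filled. The shortfall is then 0.2–0.8%. Exclusion brings a different problem: the estimated differences at 4–6 h were biased by 5–6 mm.

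**If CS or HF is used while correlation falls with lag.** Coverage at 6 h was 85–86% (100 runs, 53% / 34% rescued; Monte Carlo error √(0.86 × 0.14 / 100), about 3.5 points).

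**The case against.** The strongest reply is that the effect rests on conditions the SAP does not settle. UN is one of three AIC candidates and is not prespecified. That it wins follows from an assumed correlation that decays with lag. The model runs on the LOCF data set, and section 7.1 can be read as removing a rescued patient's record altogether, in which case nothing is left to correct. At low rescue the gain from Kenward-Roger is under one point of coverage, and where the loss is serious it does not fully cure it.

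All of this stands as a limit on size. It does not remove the point. Readings 5 minutes to 6 hours apart make decaying correlation the natural expectation. The blank trailing cells in Table 7.1 sit in the LOCF data column, while the invalid label belongs to the AUC. Section 8.1 admits to the ITT population anyone dosed with one post-baseline measurement, and section 10 assesses efficacy in it, so dropping rescued patients would sit badly with both.

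A reader might also infer that CS and HF are a written fallback if UN fails. They are not: the SAP ranks all three by AIC and has no rule for non-convergence. Nor do the documents support a claim that choosing HF makes the 5 min interval far too wide. With simulation 2's correlation and complete data, the best-fitting HF matrix gives a 5 min SE 0.99 times the true one if the VAS SD is constant, and 1.20–1.44 times if it rises from 15 to 26 mm. The SAP says nothing about how the SD changes over time.

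**Conclusion.** The point holds conditionally, as a modest and cheaply repaired weakness in a secondary analysis. It requires that UN is selected and that rescued patients contribute early readings with later ones blank. The 4–6 h intervals are then too narrow, most at 6 h. With up to roughly half of placebo patients rescued, the 6 h SE is about 1–5% too small and coverage about 93–95%. Beyond that it worsens: 91.7% at 58% placebo rescue, and 84–86% at roughly 75%. The rescue rates, VAS SDs and correlations are assumptions, since the SAP gives none of them.

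A reader might infer that the late intervals are too narrow whatever happens, or that the trial's main conclusion is at risk. Neither follows. The shortfall disappears with complete data or under the other two readings of section 7.1, and the primary ANOVA on AUC does not use this model.

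**What to change.** 1. In the section 10.2 code, replace `ddfm=satterth` with `ddfm=kr`.
2. Add to the candidate list at least one structure with time-specific variances and lag-decaying correlation, for example ANTE(1) or heterogeneous Toeplitz, and state that it is used if UN does not converge.
3. Reconcile section 7.1 and Table 7.1 with section 10.2: say whether a rescued patient's earlier readings stay in the profile models, and whether later ones are blank or filled. This choice decides whether the SE issue exists at all.

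The cost is one code option and a few sentences. Kenward-Roger is nearly neutral with complete data (SE ratio 1.002) and gives slightly wider late intervals when many patients are rescued. Under heavy rescue it still covers only about 90%, so the late intervals would need a caution in that case.
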